6.1.6. Data Adjustments/Handling/Conventions

All collected data will be presented in listings. Data not subject to analysis according to this plan will not appear in any tables or graphs but will be included only in the data listings.

6.1.7. COVID-19

A Coronavirus Disease 2019 (COVID-19) Continuity Plan has been to mitigate the negative effects of the COVID-19 pandemic on the conduct of this natural history registry.

The impact of COVID-19 on this study and participants will be described in tables and listings, and in the CSR.

The following aspects will be summarized when due to COVID-19:

- Subject who early terminated the study

- Changes to visit windows to accommodate delays for some assessments
- Protocol deviations

The situation is rapidly evolving and further updates to the COVID-19 Continuity Plan and to this SAP are possible and likely.

7. Study Subjects and Demographics

7.1. Disposition of Subjects and Withdrawals

The total number of subjects for each one of the following categories will be presented in tables:

- Consented subjects
- Screened subjects and reason for screening failure
- Enrolled subjects
- Completed subjects and reason for completion
- Reasons for study discontinuation

In summary tables for disposition of subjects, a breakdown by gender will be given.

The reason given for screening failure will be summarized in a separate table for screen failures.

7.2. Protocol Violations and Deviations

Protocol deviations will be listed.

7.3. Demographics and Other Baseline Characteristics

Summary statistics for exact age at the Baseline visit, gender, race, ethnicity, and achondroplasia familiarity will be presented by gender.

For the continuous variables, the number of non-missing values and the mean, SD, minimum, median, and maximum will be tabulated.

The number and percent of subjects reporting various medical and surgical histories, grouped by Medical Dictionary for Regulatory Activities (MedDRA) system organ class (SOC) and preferred term (PT) (coded using MedDRA v.20.0), will be tabulated by gender. Medical and surgical histories by SOC and PT will be sorted in order of descending frequency in the overall group of the SOC and then by descending frequency orders of the PT within each SOC.

8. Analysis of the Anthropometric Endpoints

Descriptive summaries of the observed value and change from baseline will be calculated for the anthropometric endpoints. For continuous variables, number of non-missing values, number of

missing values, the mean, SD, minimum, median, and maximum will be tabulated by gender. Subgroup analysis will be performed by age group at each visit.

Angles are circular quantities and are usually described using polar coordinates since the arithmetic mean may not be appropriate. However, angles for elbow and knee extension measure the deviation from a completely straight elbow or knee and are not circular quantities. The elbow extension angle and the knee extension angle will be summarized using the same descriptive statistics described for other anthropometric endpoints.

Height growth, height SDS, ration between sitting and standing heights, and ratio between arm span and standing height will be plotted against age separately by gender.

8.1. Height SDS

As a complementary descriptive analysis the height SDS will be analyzed using a Mixed Model for Repeated Measure (MMRM) based on the restricted maximum likelihood (REML) approach.

Although the SDS is calculated standardizing for age and gender, the model will include a fixed effect of gender (binary) and a random effect of age (continuous) and a random intercept for each subject.

An unstructured covariance structure will be used to model the within-subject errors. If the analysis fails to converge, simpler structures (e.g. spatial power, ante-dependent, first autoregressive) will be tested; the covariance structure converging to the best fit, as determined by Akaike's information criterion will be used. Only the final model will be included in the TLFs.

The main goal of this model is to characterize the within-subject variability, the between-subjects variability, and to address any residual effect of gender and age.

Moreover, predicted trajectories of height SDS over age will be presented in a plot separately by gender.

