8. RESEARCH METHODS

8.1. Study Design

This is a prospective, registry study, to be conducted at multiple clinical centers globally, in which participants with achondroplasia will be followed over a five-year period with respect to achondroplasia symptoms, tests & treatments, anthropometric parameters and biomarkers of bone growth collagen X, CNP/proCNP, CTX and P1NP. No study drug will be administered, and no other type of therapy will be provided.

There will be a Screening visit, a Baseline visit, 3-month interval visits (± 3 weeks) including an annual visit every 12 months and an end of study visit. The end of study visit will be scheduled (or a given visit will be considered the end of study visit) as soon as any of the following criteria is met:

- Growth plates are considered to have fused, defined as standing height gain less than 1 cm within the last 6 months;
- The participant has reached end of puberty (Tanner Stage V);
- The participant is enrolled in any interventional study;
- The participant is diagnosed or develops any of the conditions related to exclusion criteria 1, 2 & 6;
- The participant is to receive any growth hormone, insulin-like growth factor 1 (IGF-1), anabolic steroids, or any other drug expected to affect growth velocity;
- The participant has participated in the study for 5 years;

- The participant is considered lost to follow-up.

The end of this study is defined as the date of the last visit of the last child participating in the study.

The study will enroll participants in the following approximate proportions:

- 40% 0-5y;
- 40% 5-10y;
- 20% 10-15y.

Any treatment received during the study in relation to important medical events and any treatment based on the medical judgment of the investigator that may affect the participant's growth trajectory must be recorded in the eCRF:

- Description of the treatment (for medical treatment: route of administration, frequency and dose);
- Indication;
- Start and stop date.

Treatment is defined as any medical, surgical or other intervention to treat the underlying condition.

The rationale for the study design is summarised as follows:

A prospective longitudinal design is selected to collect blood samples and anthropometric data simultaneously in a standardized fashion, and thereby allowing for estimation of between and within participant variability laboratory parameters as well as testing for possible correlations between laboratory parameters and growth.

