6.1.5. Derived Variables

The following derived and computed variables have been initially identified as important for the descriptive summaries:

1. Height Growth (HG) Height Standard Deviation Score (SDS) with reference to normal population
2. Height SDS with reference to achondroplasia population
3. Sitting height/standing height (%)
4. Arm span/standing height (%)
5. Difference between arm span (cm) and standing height (cm)
6. Change from baseline = (value at current timepoint – value at baseline)
7. Average of valid anthropometric measurements. When it is required to perform 3 valid measurements, the average of the 3 will be used in descriptive summaries. If 1 or 2

valid measurement are missing, the average will include only non-missing values. If all 3 measurements are missing then the average will be missing as well.

8. Age at baseline

Age at baseline = (date of informed consent – date of birth)/365.25

Age will be rounded using 2 decimal places. If the day of birth is missing, but the month and year are present, age will be calculated based on day 1 if the month and year match the month/year of informed consent, or 15 if not. If the month is missing, age will be set to missing.

9. Exact age at each visit

- Exact age in years = (date of visit – date of birth)/365.25
- Exact age in month = (date of visit – date of birth)/30.4375
- Exact age in days = (date of visit – date of birth)

The exact age (2 decimal places if in months, 3 decimal places if in years) will be used to calculate the height-for-age SDS. The use of the 2 date variables (date of birth and date of visit) for calculating the exact age of the child is the recommended approach as best practice. If the day is missing for the date of birth, 15 will replace it, unless the month and year of birth match the month and year of informed consent in which case the first of the month will be used. If the month is missing for the date of birth, the exact age values and the height-for age SDS will be set to missing.

10. Age groups at each visit. Three age groups will be identified: <2 years, 2-10 years, and ≥10 years. Children may move from an age group to the next one during the study.

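### The height-SDS model is meant to describe within- and between-child variability, but it lets no residual variance depend on age, leaves the random-effects covariance unstated, and plans no variance output by age

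*SAP*

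**What the plan says.** SAP 8.1 introduces the model with modest status: "As a complementary descriptive analysis the height SDS will be analyzed". Its terms are given in one sentence: "the model will include a fixed effect of gender (binary) and a random effect of age (continuous) and a random intercept for each subject". The purpose is equally plain: "The main goal of this model is to characterize the within-subject variability, the between-subjects variability", followed by any residual effect of gender and age.

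On the residual side, "An unstructured covariance structure will be used to model the within-subject errors". If the model does not converge, "simpler structures (e.g. spatial power, ante-dependent, first autoregressive) will be tested" and AIC decides. No grouping of the residual variance by age is mentioned. Nothing is said about an age origin, about centring, or about the covariance between the random intercept and the random age effect. SAP 6.1.5 (item 9) defines age only as time since birth.

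The model's planned graph is of fitted values: "predicted trajectories of height SDS over age will be presented in a plot separately by gender". SAP Section 8 plans descriptive summaries by age group at each visit, and 6.1.5 (item 10) sets the groups at under 2, 2 to 10, and 10 years and over. Table 4, however, lists both height-SDS tables without age groups. SAP 8.2 applies the same model to arm span minus standing height, in cm.

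Children enter from birth to the day before the 15th birthday and stay for at most 5 years. Protocol 8.1 sets the entry mix ("The study will enroll participants in the following approximate proportions") at 40% aged 0-5, 40% aged 5-10 and 20% aged 10-15.

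**The concern.** An SDS divides height by a reference SD that grows with age. The same error in cm is therefore a larger SDS error in an infant than in a schoolchild. A residual variance that cannot follow age averages these together. Unstructured and ante-dependent forms can vary by visit number, but each visit number mixes children up to 15 years apart in age. Spatial power and AR(1) in their standard form have one variance.

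Protocol 11.5 says that the data are to be a reference for future interventional studies, and Protocol Section 6 stresses the lack of data in the youngest children. A within-child SD that is too low for them and too high for the oldest would mislead anyone who uses it for one age group.

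The between-child side raises a second question. If the two random effects are fitted as separate terms on uncentred age, the fitted between-child SD can only rise from birth, whatever the data show.

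**Working it through.** The documents state no variance figure for this model, so there is none to reproduce.

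**1. Reference SD in cm (interpolated M × S, SAP Appendix 2, boys)**

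| Reference | 1.56 years | 7.72 years | Ratio | Ratio squared |
|---|---|---|---|---|
| Achondroplasia | 70.17556 × 0.0329477 = 2.31 | 98.53881 × 0.0407461 = 4.02 | 1.737 | 3.0 |
| WHO | 82.9759 × 0.0331 = 2.75 | 125.75032 × 0.0441119 = 5.55 | 2.020 | 4.1 |

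The SDS error is the cm error divided by this SD. The ratio squared is therefore the ratio of SDS error variances for a constant cm error. An error of 0.3 cm (assumed) is 0.3/2.31 = 0.13 SDS at 1.56 years and 0.3/4.02 = 0.07 SDS at 7.72 years on the achondroplasia reference.

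**2. What one pooled within-child SD does**

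Inputs from the documents: the 40/40/20 entry mix, 3-monthly visits and 5 years of follow-up. Assumptions: entry uniform within each band, visits up to age 17, a constant 0.3 cm error, and a reference SD linear in age through the two achondroplasia values, with slope (4.015 − 2.312)/(7.721 − 1.561) = 0.276 cm per year. The pooled SD is the root of the mean variance over all visits. Visit shares are then about 3.5% under 2 years, 58.7% at 2-10 and 37.8% at 10 and over.

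For pure measurement error, the root-mean-square SDs in the three groups are 0.135, 0.086 and 0.056. Pooled: √(0.035 × 0.135² + 0.587 × 0.086² + 0.378 × 0.056²) = 0.079 to rounding. The other rows add real short-term variation (assumed) to the variance at every age.

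| Real variation added (SDS) | Pooled / true, under 2 years | Pooled / true, 10 years and over |
|---|---|---|
| 0 | 0.58 | 1.40 |
| 0.1 | 0.76 | 1.11 |
| 0.2 | 0.89 | 1.03 |

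The straight line is extrapolated beyond 7.7 years. Suppose instead that the SD stays at its 8-year value (99.6 × 0.041165 = 4.10 cm). The error at 10 years and over is then 0.3/4.10 = 0.073 SDS, the 2-10 figure is 0.087, and the pooled SD is √(0.035 × 0.135² + 0.587 × 0.087² + 0.378 × 0.073²) = 0.084. The first-row ratios become 0.084/0.135 = 0.62 and 0.084/0.073 = 1.15. The direction holds; the excess at older ages is smaller.

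**3. Between-child variance at age a**

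With age origin c, intercept variance g00, slope variance g11 and covariance g01:

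Var(a) = g00 + 2(a − c)g01 + (a − c)²g11.

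With c = 0 and g01 = 0, this is g00 + a²g11, which is smallest at birth and rises with age squared. With g01 free, the fitted curve does not depend on c.

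Simulation with REML fits: 6 data sets, 300 children, the 40/40/20 mix, 3-monthly visits over 3 years. Assumed: between-child SD 1.0 at 7.5 years, slope SD 0.08 SDS per year uncorrelated at that age, 0.5 cm error, independent residuals.

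| Between-child SD | 1 year | 7.5 years | 13 years |
|---|---|---|---|
| True | 1.13 | 1.00 | 1.09 |
| Separate effects, uncentred age | 1.10 | 1.23 | 1.45 |
| Unstructured 2x2, centred or not | 1.14 | 1.01 | 1.10 |

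In these fits the unstructured intercept SD was 1.17 uncentred (a child at birth) and 1.01 centred at 7.5 years. The fit is the same; only the age that the intercept describes changes.

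In further runs with a true SD of about 1.0 at every entry age, separate effects gave roughly 1.2 to 1.9 at 7.5 and 13 years. The unstructured matrix gave about 1.03 to 1.05, and somewhat more under the strongest assumed drift.

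**The case against.** - **The SAP is silent on the origin and covariance; it does not state a wrong choice.** This stands. It does not rule out centring or an unstructured matrix. A reader might infer that both reported variances refer to birth and to no real age band. The documents do not support that. The within-child figure is a pooled or visit-specific average, and with an unstructured matrix the between-child variance at any age follows from the fit.
- **Between-child SD need not be inflated.** This stands. With spatial-power residuals, a named fallback, and a drifting SDS, the intercept SD was 0.90 to 1.10 against a true value of about 1.0. A general claim of inflation would go too far.
- **The within-child ratios rest on assumptions.** This stands for their size. Neither the 0.3 cm error nor its constancy is in the documents, and real variation shrinks the effect. The 3.0 and 4.1 variance ratios need only a constant cm error and Appendix 2.
- **Averaging the three readings hides measurement error.** SAP 6.1.5 says "the average of the 3 will be used in descriptive summaries"; it does not fix the model input, and 8.1 does not aim to separate measurement error. Modelling individual readings is not a required change.
- **The model is complementary, and age-group summaries are planned.** Partly stands. There is no hypothesis testing, and no document says that these variances will size a trial. But Table 4 omits age groups for SDS, and descriptive SDs at a visit cannot separate within- from between-child variation.
- **The unstructured residual matrix can absorb the random intercept.** True: under the first choice the between/within split is not identified, whatever the origin. That is a separate matter, and the lack of any age dependence remains under every fallback.

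**Conclusion.** The point holds as a worthwhile, inexpensive improvement. The model's stated goal is variability, yet its residual variance cannot follow age although the SAP's own reference values imply a three- to four-fold change in SDS error variance between 1.56 and 7.72 years for a constant cm error. The direction is firm under that condition: a single figure is too low for the youngest and too high for the oldest. The size is not firm. It runs from 0.58 and 1.40 for pure measurement error to 0.89 and 1.03 with 0.2 SDS of real variation.

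On the between-child side the finding is a gap in specification. Distortion arises if the two effects are fitted as uncorrelated on uncentred age, and an unstructured 2x2 matrix largely removes it. Centred age and years since Baseline are both acceptable origins; the choice is a preference.

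For SAP 8.2, which is in cm, the SDS-scaling argument does not apply. Only the random-effects covariance, the stated origin and reporting by age group carry over.

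**What to change.** In SAP 8.1:

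1. Fit the random intercept and slope with an unstructured 2x2 covariance, and state the time origin (centred age or years since Baseline).
2. Let residual variance differ by age group at the visit, using the groups already in 6.1.5 (under 2, 2 to 10, 10 years and over). Children change group during follow-up, so say how residual correlation is handled across a change.
3. Report between- and within-child SD by those age groups. With centred age, the between-child SD follows from the variance formula above at a stated age in each group. With years since Baseline, the intercept variance pools all entry ages, so say how an age-specific figure is obtained.

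In SAP 8.2, adopt the covariance, the origin and the reporting by age group.

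The cost is SAP wording and model options on data already collected. Under spatial power or AR(1), step 2 means three residual variances in place of one. Precision under 2 years will be limited: with uniform entry, about 300 × 0.40 × 2/5 = 48 children would contribute visits there.

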8.2. Difference between Arm Span and Standing Height

The difference between the arm span and the standing height will be analyzed using the methods described in Section 8.1.

9. Safety Analysis

9.1. Related Symptoms, Tests, and Treatments

The number and percent of subjects reporting symptoms related to achondroplasia will be tabulated by gender, body system, and severity. The number and percent of subjects for each test and treatment related to achondroplasia will be described by gender.

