7.1. Achondroplasia Complications, Tests & Treatments

Achondroplasia related complications, tests and treatments will be collected in a prospective and standardized fashion to allow characterization of the natural history of the disease course in the youngest participants in relation to symptoms and development of complications, the level of actual disease burden over time due to tests and treatments, as well as data to support identification of possible risk factors.

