9.8. Achondroplasia-related Complications

Details will be collected on achondroplasia-related complications. In particular, the following complications and details will be collected at baseline and on an ongoing basis during the study.

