9.8.1. Sleep Disordered Breathing

- Has the participant ever been diagnosed with sleep-disordered breathing?
- Results of sleep tests/polysomnography including:
 - Date of test.
 - Conclusion/diagnosis of test.
 - Apnoea-hypopnoea index.
 - Was the test conducted on/off oxygen?
 - Was the test conducted on CPAP?
 - Is the test post-adenotonsillectomy (date of surgery if performed)?

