9.8.2. Otitis Media

- Has the participant ever been diagnosed with chronic otitis media (COM)?
- Were tympanostomy tubes (grommets) ever inserted (dates of insertions).
- Has the participant had hearing loss as a result of COM (including date start/end and severity)?
- Does the participant require hearing aids as a result of COM-induced hearing loss?

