9.3. Physical Examinations

The number and percent of subjects with normal, abnormal, and clinical significant results will be calculated for each body system by visit and gender.

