14.3 Safety Data			
14.3.6 Other Safety Data Summary Tables			
14.3.6.1.1	Enrolled Subjects	Achondroplasia-Related Symptoms by Body System and Severity	16.2.7.1
14.3.6.1.2	Enrolled Subjects	Achondroplasia-Related Tests	16.2.7.2
14.3.6.1.3	Enrolled Subjects	Achondroplasia-Related Treatments	16.2.7.3
14.3.6.2	Enrolled Subjects	Non-Achondroplasia-Related Conditions of Medical Significance	16.2.7.4
14.3.6.3	Enrolled Subjects	Abnormal and Clinically Significant Physical Examination Results	16.2.9.1
14.3.6.4.1	Enrolled Subjects, Age groups	Pubertal Status for Boys by Visit	16.2.9.2
14.3.6.4.2	Enrolled Subjects, Age groups	Pubertal Status for Girls by Visit	16.2.9.3
14.3.6.5	Enrolled Subjects	Concomitant Medications by ATC Level 2 and Preferred Term	16.2.9.4
14.3.6.6	Enrolled Subjects	Blood Sample Collection and X-Ray of Knees	16.2.9.5 16.2.9.6

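### SAP 9.1 sets no observation period, so its complication, test and treatment percentages mix pre-registry history with on-study events when read as written

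*SAP*

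**What the plan says.** **Analysis.** SAP 9.1 states that "The number and percent of subjects reporting symptoms related to achondroplasia will be tabulated by gender, body system, and severity", and then that "The number and percent of subjects for each test and treatment related to achondroplasia will be described by gender". The planned tables (SAP 13.1, Table 5) follow this. Table 14.3.6.1.1 is titled "Achondroplasia-Related Symptoms by Body System and Severity", and Tables 14.3.6.1.2 and 14.3.6.1.3 cover tests and treatments. None mentions visit, age group, observation period or onset. All use enrolled children.

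**Data.** Protocol 9.8 says that "the following complications and details will be collected at baseline and on an ongoing basis during the study". The schedule in Protocol Section 5 places this domain at Baseline, every 3 months and at the end of study. Some items concern the child's whole life. Protocol 9.8.1 asks "Has the participant ever been diagnosed with sleep-disordered breathing"; 9.8.2 asks the same of chronic otitis media and of tympanostomy tubes; 9.8.4 asks about any history of upper cervical compression.

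**Contrast within the SAP.** Physical examination results "will be calculated for each body system by visit and gender" (SAP 9.3). Medications are divided into prior and concomitant by consent date (SAP 9.5). Medical and surgical history has its own table (SAP 7.3, Table 14.1.3.3).

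**The concern.** A child of 12 whose tubes were placed at age 3 and a child whose tubes were placed at Month 18 can both enter the treatment table once, in the same cell. The numerator then runs from birth to last visit, while the registry observes the child only from Baseline.

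Complication data are part of the primary objective (Protocol Section 7). Protocol 7.1 promises that "Achondroplasia related complications, tests and treatments will be collected in a prospective and standardized fashion", so that the disease course and its burden over time can be described, and Protocol 11.5 says the data will serve as a reference for later interventional studies. A trial planner needs to know what children already have at entry and what they go on to develop. A pooled percentage gives neither, and it blends recalled or chart-abstracted events with events seen prospectively. Because snapshots are planned regularly (SAP 4.2), the blend also shifts from one report to the next as follow-up grows.

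**Working it through.** The documents give no event rate or sample-size calculation for this point, so there is no planned figure to reproduce. The check has two parts.

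**1. Share of the window that lies before entry**

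Inputs: age mix 40% 0-5 y, 40% 5-10 y, 20% 10-15 y (Protocol 8.1); follow-up up to 5 years (Protocol 8.1). Assumption: ages uniform within each band.

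Mean entry age = 0.4×2.5 + 0.4×7.5 + 0.2×12.5 = 6.5 years. Pre-entry share = a/(a+f), where a is mean entry age and f is years of follow-up.

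| f (years) | All | 0-5 y | 5-10 y | 10-15 y |
|---|---|---|---|---|
| 1 | 86.7% | 71.4% | 88.2% | 92.6% |
| 2 | 76.5% | 55.6% | 78.9% | 86.2% |
| 3 | 68.4% | 45.5% | 71.4% | 80.6% |
| 5 | 56.5% | 33.3% | 60.0% | 71.4% |

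If every child sat at the bottom or top of its band, mean entry age would be 4.0 or 9.0 years, and the overall 5-year share would be 4/9 = 44% or 9/14 = 64%.

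**2. What the table would show**

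Assumption: a constant first-event hazard h per year, chosen for illustration only. For a band starting at age L, the mean probability of being event-free at entry is exp(−hL) × (1 − exp(−5h))/(5h).

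With h = 0.05, this gives 0.8848, 0.6891 and 0.5367 for the three bands. Weighted: 0.4×0.8848 + 0.4×0.6891 + 0.2×0.5367 = 0.7369. Over 5 years, exp(−0.25) = 0.7788. Then:

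- Ever at Baseline: 1 − 0.7369 = 26.3%
- Pooled, birth to year 5: 1 − 0.7369×0.7788 = 42.6%
- New onset among children event-free at Baseline: 1 − 0.7788 = 22.1%
- First event on study, as a share of all enrolled: 42.6 − 26.3 = 16.3%

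Across a range of hazards, at a full 5 years:

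| h per year | Ever at Baseline | Pooled | New onset if event-free | Pooled cases with first event before entry: all / 0-5 y band |
|---|---|---|---|---|
| 0.01 | 6.2% | 10.8% | 4.9% | 57.6% / 34.1% |
| 0.02 | 11.9% | 20.3% | 9.5% | 58.7% / 34.8% |
| 0.05 | 26.3% | 42.6% | 22.1% | 61.7% / 37.1% |
| 0.10 | 43.6% | 65.8% | 39.3% | 66.3% / 40.8% |
| 0.20 | 63.7% | 86.6% | 63.2% | 73.5% / 47.9% |

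At h = 0.05 with shorter follow-up, pooled against new onset is 33.3% against 9.5% at 2 years, and 29.9% against 4.9% at 1 year.

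The share also depends on when a complication arises. With h = 0.10 acting only before age 3, 88.6% of pooled 5-year cases precede entry. With the same hazard acting only after age 8, 30.9% do.

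**The case against.** The strongest reply is that the SAP never says it pools. That is correct: pooling is inferred from silence, and the table shells are a separate document (SAP 14.1). Earlier events also have a possible home, since Protocol 9.2 records relevant past conditions and procedures and SAP 7.3 tabulates them. But nothing sends the lifetime items of Protocol 9.8 to that table or takes them out of 9.1. Each 9.1 table rests on one listing, with no filter stated, so a programmer following the text would count any record.

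The symptoms table is the weakest target. Protocol 9.8.4 asks for a mild, moderate or severe grade only for complications outside its list, so most lifetime items do not obviously feed a table by severity. This stands, and it moves the weight of the concern to diagnoses, surgery and treatments.

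Occurrence up to the last visit is a legitimate natural-history quantity in a congenital disorder, and listings are planned. It would still need a label and an age, and 9.1 gives neither.

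Two stronger readings are tempting and are not supported. A reader might infer that the percentages mainly reflect life before the registry. That holds on average under the planned mix, but not in the 0-5 year band at 5 years or for late-onset complications, and the youngest children are the protocol's main interest here. A reader might also infer that rates will be overstated several-fold, for example 11.5/5 = 2.3 times by dividing the pooled count by 5 years of follow-up. The SAP plans no such rate. At full follow-up the pooled figure is 1.4 to 2.2 times new onset across the hazards above; larger gaps arise only with short follow-up.

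**Conclusion.** The point holds as a gap in definition with a practical consequence. SAP 9.1 and its three tables state no period, and the data feeding them span lifetime history and follow-up. Taken literally, the output can be read neither as prevalence at Baseline nor as incidence on study.

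The size varies with age band, complication and snapshot, so a reader cannot undo the mixing from the published percentage. In the 5% per year illustration, 42.6% stands in for two quite different figures, 26.3% and 22.1%. These results rest on uniform ages within bands, complete follow-up to the stated year and an assumed constant hazard. The absence of a stated period rests on none of these. Since complications belong to the primary objective and the split mostly uses data already collected, the change should be made.

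**What to change.** In SAP 9.1, split each of Tables 14.3.6.1.1 to 14.3.6.1.3 into two blocks, both shown by age group:

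- **(a) History:** ever before, or present at, Baseline, as a percentage of all enrolled children.
- **(b) After Baseline, with person-years.** For complications and diagnoses, new onset among children with no history of that complication at Baseline. For tests and treatments, which can recur, any test or treatment performed after Baseline among all enrolled children, whatever their history. Restricting these to children without a history would drop repeat sleep studies and tube re-insertions, which are part of the burden the registry wants to describe.

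Base any rate over follow-up on (b) only. Adding age groups or person-years to the present tables without the split would leave the numerator unchanged.

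Assign events by date where one is collected (sleep tests, tube insertions, surgery for tibial bowing, decompression), otherwise by the visit at which the item was first reported. State how these items relate to Table 14.1.3.3, so that it is clear whether an event appears there, in 9.1 or in both.

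**Cost:** SAP wording and extra columns, with no new data collection. Counts in the post-Baseline columns will be smaller. Protocol 9.8 asks for no diagnosis date for sleep-disordered breathing, chronic otitis media, lordosis, hydrocephalus or neurodevelopmental delay, so some onsets will be misdated; a footnote should say so.
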